#### 4.5.2.1. Adverse Events of Special Interest

Adverse events of special interest will be tabulated by severity and listed separately as well. These primarily include, but are not limited to, severe reductions in platelet count ( $< 50,000 \text{ mm}^3$ ), regardless of their relationship to the Study Drug. Liver- and renal-related AEs may be considered of special interest; these may be tabulated by severity and listed separately as well.

The incidence of AEs of special interest may be plotted over time.

In addition, all bleeding AEs will be tabulated by ISIS 681257 treatment group and pooled placebo group and by the use of antiplatelet drugs. Tabulations will also be provided within cohort, by ISIS 681257 and placebo.

The results of platelet function tests (measured by the [REDACTED] instrument) will be tabulated by ISIS 681257 treatment group and pooled placebo group and by the use of antiplatelet drugs. The results of platelet function tests will be plotted by ISIS 681257 treatment group and pooled placebo group, and by use of antiplatelet drugs.

#### 4.5.3. Laboratory Data

Clinical laboratory values will be expressed in international system of units (SI).

The actual value and change (both actual and percent) from baseline to each on-study evaluation will be summarized by ISIS 681257 treatment group and pooled placebo group for each clinical laboratory parameter, including hematology, clinical chemistry, coagulation, and quantitative urinalysis. In the event of repeat values, the average of all values per study day/time will be used. For platelet counts separate summary tabulations will be provided for the results from central and local laboratories. Measurements that are unscheduled (ie, that are not on a protocol-specified visit) will not count towards the summary tabulations. Tabulations will also be provided within cohort, by ISIS 681257 and placebo.

Mean (SD) by ISIS 681257 treatment group and pooled placebo group over time will be plotted for the selected key parameters: alanine transaminase (ALT), aspartate aminotransferase (AST), alkaline phosphatase (ALP), blood urea nitrogen (BUN), bilirubin (total, direct, indirect), creatinine, hemoglobin, absolute lymphocytes and neutrophils, platelet count, and white blood cell (WBC) count.

Patients with diagnosis of Gilbert's syndrome will be excluded from the summary tabulations and plots for bilirubin (total, direct, indirect), and separate summary tabulations and plots for bilirubin values will be provided for these patients.

Shift tables for selected hematology parameters (hemoglobin, WBC and platelet count), and for selected clinical chemistry parameters (all liver and renal function tests) from baseline to last and baseline to worst value based on the on-treatment and on-study periods defined in [Section 4.5.2](#) will be provided, as appropriate. All unscheduled visits, if any, will contribute to the last or worst value. By-patient spaghetti plots of values over time will also be provided.

All laboratory data will be provided in data listings.

A subset listing will be presented for all clinically significant laboratory values.

#### 4.5.3.1. Abnormalities in Clinical Laboratory Evaluations

In addition, the number of patients who experience abnormalities in clinical laboratory evaluations will be summarized by ISIS 681257 treatment group and pooled placebo group, as well as summarized within cohort by ISIS 681257 and placebo.

#### 4.5.3.2. Liver Function Tests

The number and percent of patients falling into each of the categories below representing stopping rules will be tabulated by ISIS 681257 treatment group and pooled placebo group:

- ALT or AST > 8×Upper Limit of Normal (ULN).
- ALT or AST > 5×ULN and persists for ≥2 weeks.
- ALT or AST > 3×ULN (or the greater of 2×[Baseline Value] or 3×ULN if the baseline value was > ULN), **and** total bilirubin > 2×ULN **or** international normalized ratio (INR) > 1.5.
- ALT or AST > 3×ULN (or the greater of 2×[Baseline Value] or 3×ULN if the baseline value was >ULN), and the new appearance (ie, onset coincides with the changes in hepatic enzymes), of fatigue, nausea, vomiting, right upper quadrant pain or tenderness, fever, rash, or eosinophilia (>ULN) felt by the Investigator to be potentially related to hepatic inflammation

All events described above are required to be confirmed per the confirmation guidance described in Protocol Section 8.5.

Furthermore, the number and percent of patients who have the following reported events will be tabulated by ISIS 681257 treatment group and pooled placebo group:

- Increase in ALT or AST > ULN-3xULN
- Increase in ALT or AST > 3-5xULN
- Increase in ALT or AST > 5xULN

Box plots of ALT and AST values in terms of ULN will be plotted by ISIS 681257 treatment group and pooled placebo group at each visit.

All analyses will also be conducted within each cohort, by ISIS 681257 and placebo, as applicable.

#### 4.5.3.3. Renal Function Tests

Actual values and changes in Glomerular Filtration Rate (GFR) (estimated by the Chronic Kidney Disease –Epidemiological Collaboration [CKD-EPI] formula) will be summarized by ISIS 681257 treatment group and pooled placebo group.

The number of patients falling into each of the categories below representing monitoring rules will be tabulated by treatment group:

- eGFR decrease of > 25% from baseline.
- Urine albumin/creatinine ratio (UACR) > 250 mg/g.

- Urine protein/creatinine ratio (UPCR) > 500 mg/g.
- An increase in serum creatinine of > 0.3 mg/dL from baseline.
- An increase in serum creatinine of > 50% from baseline.
- eGFR decrease of > 40% from baseline.
- eGFR value < 45 mL/min/1.73 m^2.

All events described above are required to be confirmed per the confirmation guidance described in Protocol Section 8.5.

The number and percent of patients who have the following reported events representing stopping rules will be tabulated by ISIS 681257 treatment group and pooled placebo group:

- 24 hr creatinine clearance decrease of > 40% from baseline
- 24 hr creatinine clearance value < 45 mL/min/1.73 m^2
- 24 hr urine protein > 1g

Furthermore, the number and percent of patients who have the following reported events will be tabulated by ISIS 681257 treatment group and pooled placebo group:

- 5-fold increase from baseline in any of renal biomarkers (KIM-1, NAG, or NGAL)
- Serum creatinine increased >1-1.5 x baseline
- Serum creatinine increased >1.5-3.0 x baseline
- Serum creatinine increased >3.0 x baseline

Spaghetti plots of by-patient estimated GFR, UACR, and UPCR over time will be produced. Spaghetti plots of by-patient 24 hr creatinine clearance and any renal biomarker will be produced, if warranted.

All analyses will also be conducted within each cohort, by ISIS 681257 and placebo, as applicable.

#### 4.5.3.4. Platelet Count

The number and percent of patients falling into each of the categories below will be tabulated by ISIS 681257 treatment group and pooled placebo group:

- Platelet count decrease below LLN.
- Platelet count decrease of  $\geq 30\%$  from baseline.

All events described above are required to be confirmed per the confirmation guidance described in Protocol Section 8.5.

Furthermore, the number and percent of patients who have the following reported events will be tabulated by ISIS 681257 treatment group and pooled placebo group, and separately for the subset of patients with normal baseline ( $\geq 140,000/\text{mm}^3$ ):

- Any 2 occurrences of platelet count < 140,000/mm^3

- Any single occurrence of platelet count  $< 100,000/\text{mm}^3$
- Any 2 occurrences of platelet count  $< 140,000/\text{mm}^3$  or any single occurrence of platelet count  $< 100,000/\text{mm}^3$
- Platelet count  $< 140,000$  but  $\geq 100,000/\text{mm}^3$
- Platelet count  $< 100,000$  but  $\geq 75,000/\text{mm}^3$
- Platelet count  $< 75,000$  but  $\geq 50,000/\text{mm}^3$
- Platelet count  $< 50,000/\text{mm}^3$
- Platelet count decrease of  $\geq 30\%$  from baseline
- Platelet count decrease of  $\geq 50\%$  from baseline

Additionally, the analysis above will be performed for patients with baseline platelet count of  $\geq 160,000/\text{mm}^3$ , and those with baseline platelet count  $< 160,000/\text{mm}^3$ .

Plots of platelet count, change from baseline in platelet count, and percent change from baseline in platelet count over time will be generated for each treatment group and pooled placebo group.

Time to platelet count  $< 100,000/\text{mm}^3$  will be performed if warranted.

All analyses will also be conducted within each cohort, by ISIS 681257 and placebo, as applicable.

#### 4.5.4. Vital Signs and Physical Examinations

The actual value and change from baseline to each on-study evaluation will be summarized for vital signs by ISIS 681257 treatment group and pooled placebo group.

Mean (SD) values by treatment group and by-patient spaghetti plots over time of weight and BMI will be produced.

Vital sign measurements and changes from baseline will be presented for each patient in data listings.

Any abnormalities in physical examination deemed clinically significant by the Investigator will be reported as adverse events. All physical examination dates will be presented in a data listing.

#### 4.5.5. Electrocardiogram

Average of triplicate ECG results will be summarized using descriptive statistics of actual values and changes from baseline at each on-study visit by ISIS 681257 treatment group and pooled placebo group. Responses to overall interpretation will be tabulated by counts and percentages at each on-study visit.

Furthermore, the number and percent of patients who have the following reported events will be tabulated by ISIS 681257 treatment group and pooled placebo group:

- Absolute QT/QTc  $> 450$  msec
- Absolute QT/QTc  $> 480$  msec

- Absolute QT/QTc >500 msec
- Increase from baseline in QT/QTc >30 ms
- Increase from baseline in QT/QTc >60 ms
- Increase from baseline in PR ≥ 50% (if absolute baseline < 200ms)
- Increase from baseline in PR ≥ 25% (if absolute baseline > 200ms)
- Increase from baseline in QRS ≥ 50% (if absolute baseline < 100ms)
- Increase from baseline in QRS ≥ 25% (if absolute baseline > 100ms)

ECG data for each patient will be provided in a data listing.

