### **3.8. Subpopulations**

Subgroup analyses using pooled data for the primary and secondary efficacy endpoints as well as TEAE incidences are planned as follow:

- By age (age categories <65 and ≥ 65 years old)
- By gender

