#### 4.5.1. Study Drug Exposure

Study drug exposure will be calculated as the number of days patients were administered study drug, as determined below, and will be summarized by ISIS 681257 treatment group and pooled placebo group using descriptive statistics.

*Duration of Study Drug Exposure (days) = (Date of last dose – Date of first dose) + 1*

Duration of study drug exposure will also be presented in the following categories: ≤13 weeks, >13 to ≤26 weeks, >26 to ≤30 weeks, >30 to ≤34 weeks, >34 to ≤38 weeks, >38 to ≤42 weeks, >42 to ≤46 weeks, >46 to ≤50 weeks, and >50 weeks.

Percent compliance will be summarized for each patient from date of first dose through the treatment period per the following definition:

$$\text{Percent Compliance (\%)} = \frac{\text{Total Number of Infusions Received}}{\text{Total Number of Infusions Planned Per Protocol}} \times 100\%$$

Patient compliance with study drug will be summarized by treatment groups and pooled placebo group and presented in a by-patient data listing. For patients who withdrew/discontinued treatment early, the volume of study drug planned will be calculated based on the period on-treatment up to their withdrawal/termination.

The proportion of patients with compliance ≥ 80% and <80% will be calculated.

Total drug received will be summarized by treatment group and pooled placebo group. Actual dose intensity, defined as the ratio of total drug received and the actual duration of treatment (in weeks), and relative dose intensity, defined as the ratio of actual dose intensity and planned dose intensity, will be summarized by ISIS 681257 treatment group and pooled placebo group.

Duration of study drug exposure (in days and in weeks), percent compliance, total drug received, actual dose intensity and relative dose intensity for each patient will also be provided in data listings.

In addition to the Safety Set, all exposure analyses will be performed using the FAS as well.

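### The paired PR and QRS event rows leave a baseline of exactly 200 ms (PR) or 100 ms (QRS) in neither row of its pair

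*SAP*

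**What the plan says.** SAP Section 4.5.5 lists nine ECG event rows, to be tabulated as number and percent of patients by active treatment group and pooled placebo. Five concern QT/QTc. The other four form two pairs:

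- PR: "Increase from baseline in PR ≥ 50% (if absolute baseline < 200ms") and "Increase from baseline in PR ≥ 25% (if absolute baseline > 200ms").
- QRS: "Increase from baseline in QRS ≥ 50% (if absolute baseline < 100ms") and "Increase from baseline in QRS ≥ 25% (if absolute baseline > 100ms").

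The same section provides three other views of the ECG data. Continuous values: "Average of triplicate ECG results will be summarized using descriptive statistics of actual values and changes from baseline". The reader's assessment: "Responses to overall interpretation will be tabulated by counts and percentages at each on-study visit". There is also a by-patient listing.

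Section 3.4 takes the ECG baseline as the last non-missing assessment before the first dose. It has no rule for a value that falls on a cut-off.

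**The concern.** Each pair is meant to apply one percentage limit to patients with a shorter baseline interval and a stricter one to patients with a longer interval. For that to work, every baseline value must belong to one side. With strict signs on both sides, the cut-off value belongs to neither.

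The SAP closes its other two-way splits. For age: "By age (age categories <65 and ≥ 65 years old"). For compliance: "The proportion of patients with compliance ≥ 80% and <80% will be calculated". The baseline platelet split at 160,000/mm³ (Section 4.5.3.4) and the baseline Lp(a) split at 70 mg/dL (supplement, Additional Subgroups) are closed too. Nothing suggests that the ECG gap was intended.

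At stake is a conduction event missing from its table because the baseline happened to be a round number. A programmer must either follow the text and drop the event or pick a side without documentation. Safety and tolerability are part of the primary objective (Section 1.1.2.1), so the table should count what it sets out to count.

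**Working it through.** The plan gives no figure to reproduce here. The check has two parts: whether the rows miss a value, and how often that could matter.

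**1. Applying the rows as written.** A PR event is counted if (baseline < 200 and increase ≥ 50%) or (baseline > 200 and increase ≥ 25%). QRS follows the same form with 100 in place of 200.

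| Baseline | Smallest increase counted |
|---|---|
| PR 199.67 ms | 50% |
| PR 200 ms | none; not counted even at +100% |
| PR 200.33 ms | 25% |
| QRS 99.67 ms | 50% |
| QRS 100 ms | none; not counted even at +100% |
| QRS 100.33 ms | 25% |

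For example, PR going from 200 to 300 ms is (300 − 200)/200 = +50%. QRS going from 100 to 150 ms is (150 − 100)/100 = +50%. Each meets both percentage limits of its pair and enters neither row of it.

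**2. How many patients could be affected.** Only the planned total of about 270 (Section 3.1) comes from the SAP. The rest is assumed:

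- PR baseline: mean 160, 170 or 180 ms; SD 20, 25 or 30 ms.
- QRS baseline: mean 90, 95 or 100 ms; SD 10, 12 or 15 ms.
- Both normal and independent of each other.
- Recording step r: 1/3 ms if the rows use an unrounded average of three whole-millisecond readings, 1 ms if they use a single reading. Section 4.5.5 applies the triplicate average to the continuous summaries and does not say what the event rows use.

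Share on a cut-off c: Φ((c + r/2 − mean)/SD) − Φ((c − r/2 − mean)/SD). Call this p for PR and q for QRS. Share on at least one cut-off: p + q − pq.

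| Case | Step | p | q | p + q − pq | × 270 |
|---|---|---|---|---|---|
| Lowest (PR 160/20, QRS 90/15) | 1/3 ms | 0.090% | 0.710% | 0.80% | 2.16 |
| Central (PR 170/25, QRS 95/12) | 1/3 ms | 0.259% | 1.016% | 1.272% | 3.44 |
| Highest (PR 180/20, QRS 100/10) | 1/3 ms | 0.403% | 1.330% | 1.73% | 4.66 |
| Lowest | 1 ms | 0.270% | 2.129% | 2.39% | 6.46 |
| Central | 1 ms | 0.777% | 3.047% | 3.800% | 10.26 |
| Highest | 1 ms | 1.210% | 3.988% | 5.15% | 13.90 |

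The last column uses unrounded shares.

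**3. Events lost.** Assume that 1% to 5% of boundary patients rise by at least 25%, and that the 25% limit is the one that should apply to them.

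- 1/3-ms step: 2.16 × 1% = 0.02 to 4.66 × 5% = 0.23.
- 1-ms step: 6.46 × 1% = 0.06 to 13.90 × 5% = 0.70.

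If the 50% limit was meant for boundary patients, fewer are lost.

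**The case against.** The strongest objection is that nothing turns on this. Formal testing is confined to the primary and selected secondary efficacy endpoints (Section 3.2), and the stopping rules are hepatic, renal and platelet (Section 1.2.3). A large PR or QRS rise in a boundary patient would still appear in the change-from-baseline summaries and the listing, and the overall interpretation is tabulated at each visit. A programmer would probably notice the gap, and Section 5 asks for deviations from planned analyses to be documented when they are made. Apart from the 270, every input to the size estimate is assumed. All of this stands, and it puts the point at the lowest level of importance. It does not make the rows right as written.

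Three stronger readings are tempting and are not supported:

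- *The patient disappears from the ECG event table.* A patient with PR of exactly 200 ms remains eligible for all five QT/QTc rows and for the QRS pair. One with QRS of exactly 100 ms remains eligible for the QT/QTc rows and the PR pair. Only the pair concerned is affected.
- *The percentages are biased because boundary patients stay in the denominator.* Section 4.5.5 gives no denominator for these rows. It could be all patients in the group or only those in the row's baseline stratum.
- *The upper rows were meant to read ≥.* The SAP does not show which side was to include the cut-off.

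Text damage from the PDF is an unlikely explanation. The same strict pattern occurs in two separate pairs, and the ≥ sign was read correctly in all four lines.

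**Conclusion.** The point holds as a small error in a tabulation rule. Followed as written, Section 4.5.5 cannot count a PR increase for a patient with a baseline of exactly 200 ms, or a QRS increase for one at exactly 100 ms, and no other section assigns these values to a row. Both values can occur, whether the rows use single readings or triplicate averages.

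That conclusion rests on the text alone. The size rests on assumed baseline distributions, recording step and event rate. On those, between about 2 and 14 of 270 patients fall on a boundary, and fewer than one event is expected to be lost in the whole trial. No efficacy result, test or stopping rule in the SAP depends on these counts.

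**What to change.** Close one side of each pair. The preferred change is baseline ≥ 200 ms in the 25% PR row and baseline ≥ 100 ms in the 25% QRS row. This is conservative for safety, because a boundary patient is then flagged from the smaller increase. Writing ≤ 200 ms and ≤ 100 ms in the 50% rows closes the gap equally well, but such a patient is then flagged only from +50%. The sponsor should choose one and record it. Either way, every patient with a baseline value falls in exactly one row of each pair.

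The cost is one inequality sign in each of two rows, in the SAP wording and the table program. No new data are needed. The supplement that already redefines compliance shows that a change of this size can be made without reissuing the SAP.

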#### 4.5.6. Prior and Concomitant Medications

Prior and concomitant medications will be coded using the WHO Drug Dictionary (Version March 2017). Results will be tabulated by anatomic therapeutic class (ATC) and preferred term. Patients will be counted only once by ATC and preferred term. Missing and partial dates will be handled as described in [Section 3.10.3](#).

Concomitant medications will be tabulated by ISIS 681257 treatment group and pooled placebo group, where any medications that did not end prior to first dose will be included. Prior medications consist of all medication that ended prior to the first dose. If an end date is missing or the medication is ongoing, the medication will be included.

The use of prior and concomitant medications will be included in a by-patient data listing.

## **5. CHANGES TO PLANNED ANALYSES**

All changes from procedures outlined in the protocol and procedures outlined in this SAP will be summarized in the study report. Decisions to deviate from planned analyses will be documented at the time they are made.

If any modifications in the experimental design, dosages, parameters, patient selection, or any other sections of the protocol are indicated or required, the Investigator will consult with the Sponsor before such changes are instituted. Modifications will be accomplished through formal amendments to this protocol by the Sponsor and approval from the appropriate Institutional Review Board (IRB) or Independent Ethics Committee (IEC).

## 7. APPENDIX 1: GRADING SCALE FOR ADVERSE EVENTS RELATING TO LABORATORY ABNORMALITIES

The following grading recommendations for AEs relating to laboratory test abnormalities are based upon the Common Terminology Criteria for Adverse Events (CTCAE) v4.03, June 2010.

Adverse Event	Mild	Moderate	Severe
Hematology			
aPTT prolonged	>ULN – 1.5 × ULN	>1.5 – 2.5 × ULN	>2.5 × ULN; hemorrhage
Eosinophils increased †	650 – 1,500 cell/mm 	1,501 – 5,000 cell/mm 	>5,000 cell/mm 
Fibrinogen decreased	<1.0 – 0.75 × LLN or <25% decrease from baseline	<0.75 – 0.5 × LLN or 25 - <50% decrease from baseline	<0.5 × LLN or ≥50% decrease from baseline
Hemoglobin decreased (Anemia)	Hemoglobin (Hgb) <LLN – 10.0 g/dL; <LLN – 6.2 mmol/L; <LLN – 100 g/L	Hgb <10.0 – 8.0 g/dL; <6.2 – 4.9 mmol/L; <100 – 80 g/L	Hgb <8.0 g/dL; <4.9 mmol/L; <80 g/L; transfusion indicated
Hemoglobin increased	Increase in >0 – 2 g/dL above ULN or above baseline if baseline is above ULN	Increase in >2 – 4 g/dL above ULN or above baseline if baseline is above ULN	Increase in >4 g/dL above ULN or above baseline if baseline is above ULN
INR increased	>1 – 1.5 × ULN; >1 – 1.5 times above baseline if on anticoagulation	>1.5 – 2.5 × ULN; >1.5 – 2.5 times above baseline if on anticoagulation	>2.5 × ULN; >2.5 times above baseline if on anticoagulation
Lymphocyte count decreased	<LLN – 800/mm  ; <LLN – 0.8 × 10  /L	<800 – 500/mm  ; <0.8 – 0.5 × 10  /L	<500/mm  ; <0.5 × 10  /L
Lymphocyte count increased	-	>4000/mm  – 20,000/mm 	>20,000/mm 
Neutrophil count decreased	<LLN – 1500/mm  ; <LLN – 1.5 × 10  /L	<1500 – 1000/mm  ; <1.5 – 1.0 × 10  /L	<1000/mm  ; <1.0 × 10  /L
Platelet count decreased	<LLN – 75,000/mm  ; <LLN – 75.0 × 10  /L	<75,000 – 50,000/mm  ; <75.0 – 50.0 × 10  /L	<50,000/mm  ; <50.0 × 10  /L
White blood cell decreased	<LLN – 3000/mm  ; <LLN – 3.0 × 10  /L	<3000 – 2000/mm  ; <3.0 – 2.0 × 10  /L	<2000/mm  ; <2.0 × 10  /L
Chemistry			
Acidosis	pH <normal, but ≥7.3	-	pH <7.3
Alanine aminotransferase increased	>ULN – 3.0 × ULN	>3.0 – 5.0 × ULN	>5.0 × ULN
Alkaline phosphatase increased	>ULN – 2.5 × ULN	>2.5 – 5.0 × ULN	>5.0 × ULN
Alkalosis	pH >normal, but ≤7.5	-	pH >7.5
Aspartate aminotransferase increased	>ULN – 3.0 × ULN	>3.0 – 5.0 × ULN	>5.0 × ULN

Adverse Event	Mild	Moderate	Severe
Blood bilirubin increased	>ULN – 1.5 × ULN	>1.5 – 3.0 × ULN	>3.0 × ULN
Cardiac troponin I increased	Levels above the upper limit of normal and below the level of myocardial infarction as defined by the manufacturer	-	Levels consistent with myocardial infarction as defined by the manufacturer
Cardiac troponin T increased	Levels above the upper limit of normal and below the level of myocardial infarction as defined by the manufacturer	-	Levels consistent with myocardial infarction as defined by the manufacturer
CD4 lymphocytes decreased	<LLN – 500/mm  ; <LLN – 0.5 × 10  /L	<500 – 200/mm  ; <0.5 – 0.2 × 10  /L	<200/mm  ; <0.2 × 10  /L
CPK increased*	>ULN - <6 ULN	6 – 10 × ULN	>10 × ULN
Creatinine increased	>1 – 1.5 × baseline; >ULN – 1.5 × ULN	>1.5 – 3.0 × baseline; >1.5 – 3.0 × ULN	>3.0 × baseline; >3.0 × ULN
GGT increased	>ULN – 2.5 × ULN	>2.5 – 5.0 × ULN	>5.0 × ULN
Hypercalcemia	Corrected serum calcium of >ULN – 11.5 mg/dL; >ULN – 2.9 mmol/L; Ionized calcium >ULN – 1.5 mmol/L	Corrected serum calcium of >11.5 – 12.5 mg/dL; >2.9 – 3.1 mmol/L; Ionized calcium >1.5 – 1.6 mmol/L; symptomatic	Corrected serum calcium of >12.5 mg/dL; >3.1 mmol/L; Ionized calcium >1.6 mmol/L; hospitalization indicated
Hyperglycemia	Fasting glucose value >ULN – 160 mg/dL; Fasting glucose value >ULN – 8.9 mmol/L	Fasting glucose value >160 – 250 mg/dL; Fasting glucose value >8.9 – 13.9 mmol/L	>250 mg/dL; >13.9 mmol/L; hospitalization indicated
Hyperkalemia	>ULN – 5.5 mmol/L	>5.5 – 6.0 mmol/L	>6.0; hospitalization indicated
Hypermagnesemia	>ULN – 3.0 mg/dL; >ULN – 1.23 mmol/L	-	>3.0 mg/dL; >1.23 mmol/L
Hypernatremia	>ULN – 150 mmol/L	>150 – 155 mmol/L	>155 mmol/L; hospitalization indicated
Hyperuricemia	>ULN – 10 mg/dL (0.59 mmol/L) without physiologic consequences	-	>ULN – 10 mg/dL (0.59 mmol/L) with physiologic consequences
Hypoalbuminemia	<LLN – 3 g/dL; <LLN – 30 g/L	<3 – 2 g/dL; <30 – 20 g/L	<2 g/dL; <20 g/L
Hypocalcemia	Corrected serum calcium of <LLN – 8.0 mg/dL; <LLN – 2.0 mmol/L; Ionized calcium <LLN – 1.0 mmol/L	Corrected serum calcium of <8.0 – 7.0 mg/dL; <20 – 1.75 mmol/L; Ionized calcium <1.0 – 0.9 mmol/L; symptomatic	Corrected serum calcium of <7.0 mg/dL; <1.75 mmol/L; Ionized calcium <0.9 mmol/L; hospitalization indicated
Hypoglycemia	<LLN – 55 mg/dL; <LLN – 30 mmol/L	<55 mg/dL; <3.0 mmol/L	<40 mg/dL (<2.2 mmol/L) AND requires assistance of another person to actively administer carbohydrates, glucagon, or take other corrective actions‡
Hypokalemia	<LLN – 3.0 mmol/L	<LLN – 3.0 mmol/L; symptomatic; intervention indicated	<3.0 mmol/L; hospitalization indicated

Adverse Event	Mild	Moderate	Severe
Hypomagnesemia	<LLN – 1.2 mg/dL; <LLN – 0.5 mmol/L	<1.2 – 0.9 mg/dL; <0.5 – 0.4 mmol/L	<0.9 mg/dL; <0.4 mmol/L
Hyponatremia	<LLN – 130 mmol/L	-	<130 mmol/L
Hypophosphatemia	<LLN – 2.5 mg/dL; <LLN – 0.8 mmol/L	<2.5 – 2.0 mg/dL; <0.8 – 0.6 mmol/L	<2.0 mg/dL; <0.6 mmol/L
Lipase increased	>ULN – 1.5 × ULN	>1.5 – 2.0 × ULN	>2.0 × ULN
Serum amylase increased	>ULN – 1.5 × ULN	>1.5 – 2.0 × ULN	>2.0 × ULN
Urine			
Proteinuria			
Adults	1+ proteinuria; urinary protein <1.0 g/24 hrs	2+ proteinuria; urinary protein 1.0 – 3.4 g/24 hrs	Urinary protein ≥3.5 g/24 hrs
Children	-	Urine P/C (Protein/Creatinine) ratio 0.5 – 1.9	Urine P/C >1.9
Hematuria	Asymptomatic; clinical or diagnostic observations only; intervention not indicated	Symptomatic; urinary catheter or bladder irrigation indicated	Gross hematuria; transfusion, IV medications or hospitalization indicated; elective endoscopic, radiologic or operative intervention indicated

- † Grading for this parameter is derived from the Toxicity Grading Scale for Healthy Adult and Adolescent Volunteers Enrolled in Preventive Vaccine Clinical Trials, Sept 2007.
- \* Grading for this parameter is derived from the Division of AIDS (DAIDS) Table for Grading the Severity of Adult and Pediatric Adverse Events Version 2.0, Nov 2014.
- ‡ Modified for consistency with the ADA and Endocrine Society Guidelines (Seaquist ER, Anderson J, Childs B, et al. Hypoglycemia and Diabetes: A Report of a Workgroup of the American Diabetes Association and The Endocrine Society. *Diabetes Care* 2013;36: 1384-95).

